Of the thirteen patients who agreed to participate, six were randomized to emergency room treatment and seven were randomized to operating room treatment. One of the patients, randomized to operating room treatment fracture was NOT found to have an open fracture and

will be eliminated from final formal assessment beyond intent to treat analysis. Another patient who was randomized to the operating room chose not to undergo surgery and instead received ED treatment only. None of the twelve patients' fractures, enrolled in the study, were complicated by infection or delayed healing. There have been no differences in anesthesia/sedation related complications.

E. Methods:

Clinical Trial Portion

Design of the study: A prospective, randomized unblinded non-inferiority clinical trial of children with Type I open fractures to evaluate whether emergency room management and close follow up will not be inferior to formal operative irrigation and debridement in terms of infection rates and bone healing times. The baseline rate of infection with open fractures, treated operatively, is noted to be 0-10% in the literature. We will choose a baseline infection rate of 1%.

Study population:

Inclusion Criteria - Patients will be included if their age is between 3 and 14 years, if the fracture is amenable to treatment by closed reduction, a low energy injury (falls from less than 10 feet, bicycle accidents), wounds less than 1 cm in length and the bone not visualized through the skin.

Exclusion Criteria - Patients will be excluded if they do not meet inclusion criteria, if the fracture would typically require operative reduction and fixation, if their mechanism was high energy (struck by vehicle, motor vehicle accidents, fall from height greater than 10 feet), if there is gross contamination of the wound, or if the open injury involved the hands or feet (the current standard of care to treat open injuries involving hands or feet is only emergency room management).

Study Procedures:

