Patients will be recruited from the emergency department at the participating hospitals. All patients with open fractures (fractures associated with a skin wound) who present to emergency department will be assessed for inclusion. The initial assessment of open fracture will be identified by the emergency room physician who will discuss with the attending on call. The orthopaedic attending will determine if this child is amenable to non-operative treatment and would be considered for study inclusion.

All children will be given antibiotics (Ancef 25mg/kg up to 1gm, or clindamycin if allergic to first generation cephalosporin or penicillin) and if the inclusion criteria are met, will be offered to participate in the study by the orthopaedic surgeon or their delegate. If the patient refused study inclusion, they will then be treated per the attending treating physician recommendation.

If the patient agrees to participate he/she will be randomized. The randomization chart is saved in the REDCap database and functions to randomly assign a patient who is entered into the database into a treatment group, stratifying by site. The attending physician will be responsible for determining the randomization assignment by either (1) logging into the REDCap database to enter the patient and randomize them or (2) calling the research coordinator or his/her representative who will then log in to REDCap to randomize the patient. As a backup, the research coordinator will have the randomizations for each site in numbered, sealed envelopes. The study coordinator will be available 24 hours a day to provide the randomization assignment, the consent form (see consent process below), and answer questions prior to treatment arm assignment. Children in both arms of the study will receive emergency room irrigation with one liter of normal saline, realignment/reduction of the fracture, and casting. Conscious sedation will

usually be necessary for this to occur. Patients will be admitted and have up to 24 hours from the time of injury to make a final decision.

No difference in outcomes have been shown in patients with open fractures treated with operative debridement in less than 6 hours compared with those treated from 6 to 24 hours.(8) The surgical timing will be determined by the attending orthopaedic surgeon.

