We will use an independent two-sample confidence interval for binomial proportions comparing infection rates between the two treatment arms. If the upper limit of a two-sided, 95% confidence interval is less than the margin of non-inferiority, we will have evidence that ED management is not inferior to OR management. Similarly, an independent two-sample confidence for difference in mean healing time will be constructed and used in the same manner to determine evidence of non-inferiority. Both large sample, normal approximation methods and exact methods will be explored. Descriptive data will be used to relay anesthesia complications, additional procedures and significant infections. Primary analysis will be based on the "as treated" principle, and an intent-to-treat analysis will also be conducted. We expect almost no cross-over in the initial 24 hours after injury. We will also use Kaplan-Meier estimation to create curves comparing cumulative incidence of infection as well as time to healing for the duration of study follow-up.

Data Security:

Research Electronic Data Capture (REDCap)

REDCap is a secure application used for managing online databases for collecting research data. The software allows data to be stored over a secure web connection with authentication and data logging features. The database creates a log of all activity including information such as the date, time and user who performed the action. The database is password protected and only approved users are able to access projects through REDCap. Data for all sites involved in this multi-center project will be stored in this electronic database. PIs and research coordinators from each site

will be assigned Northwestern University Affiliate NetIDs which will give them access to REDCap through Northwestern University Clinical and Translational Sciences Institute (NUCATS). Once these NetIDs are granted, the research coordinator at Lurie Children's will then add these individuals to the REDCap project.

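### A single as-treated comparison is the only primary analysis for non-inferiority, with no role for intention-to-treat and no rule if the two disagree

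*Combined protocol and SAP*

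**What the plan says.** - **Analysis set.** E. Methods, Data Analysis (after Data management): "Primary analysis will be based on the 'as treated' principle, and an intent-to-treat analysis will also be conducted". The next sentence reads: "We expect almost no cross-over in the initial 24 hours after injury".
- **Decision rule.** The same section, and Sample size assumptions and estimates, declare non-inferiority when the upper limit of a two-sided 95% interval for the difference in infection proportions is below the margin (4 percentage points). Neither place names the analysis set.
- **Design.** Design of the study: "A prospective, randomized unblinded non-inferiority clinical trial of children with Type I open fractures". Study Procedures: "Patients will be admitted and have up to 24 hours from the time of injury to make a final decision".
- **Pilot.** D. Previous Work: "six were randomized to emergency room treatment and seven were randomized to operating room treatment". On crossover: "Another patient who was randomized to the operating room chose not to undergo surgery and instead received ED treatment only". On eligibility: "One of the patients, randomized to operating room treatment fracture was NOT found to have an open fracture"; that child "will be eliminated from final formal assessment beyond intent to treat analysis".
- **Hints at a definition.** Experimental and Control Interventions describes two randomised arms and places OR treatment within 24 hours. Ascertainment of response variables counts a return to the operating room for a wound complication after randomisation as an infection. No sentence turns these hints into a definition of treatment received.

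**The concern.** Randomisation protects a comparison of children as assigned. Once children are regrouped by the treatment they received, the groups can differ in ways that bear on infection risk. Here families and surgeons know the assignment, and families have time to change course.

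ITT does not solve this alone in a non-inferiority trial. Children who cross over make the arms more alike, which favours the claim. Each analysis can therefore mislead, in ways that depend on who crosses. The plan rests the claim on one of them and leaves the other without a function.

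At about 1% infection and 150 children per arm, only one or two infections per arm are expected (150 × 0.01 = 1.5). The classification of a few children can then settle the trial's main conclusion. If the analyses differ, the choice between them would be made after the data are known.

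**Working it through.** **1. The plan's own figure.** Inputs from Sample size assumptions and estimates: 150 per arm, 1% in both arms, margin 0.04, one-sided 2.5%. With p and q the ED and OR proportions, and n and m the group sizes, the upper limit is

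U = p − q + 1.96 × √[p(1−p)/n + q(1−q)/m].

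Summing the binomial probabilities of all outcomes with U < 0.04 gives power 0.9105, against 0.9111 in the plan's table. The plan's figure is reproduced, so this unpooled normal-approximation (Wald) limit is used below. At true rates of 5% (ED) and 1% (OR), where the claim is false, it passes in 5.2% of trials. That excess over 2.5% comes from the interval and is a separate issue.

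**2. What the pilot shows about crossover** (exact Clopper-Pearson 95% intervals):

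- OR to ED: 1/7 = 14% (0.4% to 58%)
- All randomised: 1/13 = 7.7% (0.2% to 36%)
- ED to OR: none reported, 0/6 (0% to 46%)

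These counts neither support almost no crossover nor fix any other rate. The groups do shift: 6 ED and 7 OR as randomised become 6 + 1 = 7 ED and 7 − 1 − 1 = 5 OR, after moving the crossover and removing the child without an open fracture.

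**3. How few children reverse a borderline result** (ED first, margin 4%):

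| Case | ITT | U | As-treated | U |
|---|---|---|---|---|
| 3 uninfected OR-assigned children treated in ED | 4/150 vs 3/150 | 4.08% fails | 4/153 vs 3/147 | 3.98% passes |
| 1 infected OR-assigned child treated in ED | 3/150 vs 2/150 | 3.56% passes | 4/151 vs 1/149 | 4.86% fails |
| 21 uninfected OR-assigned children (1/7) treated in ED | 4/150 vs 2/150 | 4.50% fails | 4/171 vs 2/129 | 3.90% passes |

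First row, ITT: 0.667% + 1.96 × 1.743% = 4.08%. As-treated: 0.574% + 1.96 × 1.739% = 3.98%.

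**4. How often false claims arise.** Assumptions, not in the documents: 20% of children carry five times the risk of the rest; risk follows the treatment received; true rates are 5% and 1%; 1/7 of OR-assigned children cross to ED; 60,000 simulated trials per scenario.

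The expected differences show the mechanism. Average relative risk is 0.8 × 1 + 0.2 × 5 = 1.8, so low-risk children have 1/1.8 = 0.556 and high-risk children 5/1.8 = 2.778 times the average. About 150/7 = 21.43 children cross.

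- *Random crossers.* As-treated: 5% − 1% = 4.00 points. ITT: 5% − (6/7 × 1% + 1/7 × 5%) = 3.43.
- *Low-risk crossers.* Expected infections are 21.43 × 5% × 0.556 = 0.595 among crossers and 1.5 − 21.43 × 1% × 0.556 = 1.381 among those who stay in OR. As-treated: (7.5 + 0.595)/171.43 − 1.381/128.57 = 4.72% − 1.07% = 3.65. ITT: 5% − (1.381 + 0.595)/150 = 3.68.
- *High-risk crossers.* The same steps give 2.976 and 0.905. As-treated: 10.476/171.43 − 0.905/128.57 = 6.11% − 0.70% = 5.41. ITT: 5% − 3.881/150 = 2.41.

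| Who leaves OR (1/7) | As-treated | ITT | Both required |
|---|---|---|---|
| Random | 4.4% | 7.3% | 3.1% |
| Low-risk | 6.1% | 6.1% | 4.0% |
| High-risk | 0.9% | 12.9% | 0.8% |

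The no-crossover rate in the simulation is about 5.3%. In these three rows as-treated passes while ITT fails in 1.3%, 2.1% and 0.1% of trials; the reverse occurs in 4.1%, 2.1% and 12.1%. With 1% crossing from OR to ED, the two disagree in at most 1.3% of trials.

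**The case against.** **As-treated may be the better single choice.** In the only crossover direction seen in the pilot, it has false-claim rates equal to or below those of ITT. This stands. A reader might infer that ITT should simply replace as-treated as primary; the calculations do not support that.

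**The plan does not say that a contrary ITT result would be ignored.** A reader might infer that as-treated prevails even when ITT fails. No sentence says so, and both analyses are planned. What the text supports is narrower: one primary analysis, no decision role for ITT, and silence on disagreement.

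**The meaning of as-treated is largely implied.** The sections cited above point to initial treatment within 24 hours, in randomised arms, with later returns to the operating room as outcomes. A reader might infer that children in the non-randomised chart review could enter the as-treated groups, because the same data are collected on them. That is not the natural reading, since the analysis compares the two treatment arms. An explicit sentence is still missing.

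**The crossover evidence is one child, and the reversal examples sit near the margin.** Both are true. The examples show that a reversal is possible, not that it is likely, and the simulated rates depend on assumed crossover and risk patterns.

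**Conclusion.** The point holds as a gap in the decision rule: a single comparison formed after randomisation carries the non-inferiority claim, with no rule for disagreement and an expectation about crossover that the pilot does not establish. It is not a finding that as-treated is worse than ITT, and the direction of any bias is unknown.

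The size depends on crossover. Under the assumed 1/7 from OR to ED, requiring both analyses lowers the false-claim rate from 4.4%, 6.1% and 0.9% (as-treated alone) to 3.1%, 4.0% and 0.8%. Part of that gain is automatic, because a joint rule cannot exceed either component. If crossover is about 1%, the choice hardly matters. The stated power is not in question. This is a cheap improvement.

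**What to change.** In the Data Analysis section:

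- Claim non-inferiority on infection only if the upper 95% limit is below the 4% margin in both (a) ITT, with all randomised children by assigned arm, and (b) the analysis by treatment received. A per-protocol set kept within the randomised arms is an acceptable alternative for (b).
- Define treatment received as the initial treatment within the plan's own 24-hour window, in randomised children only. Count any later return to the operating room as an outcome, never as a change of arm.
- Report crossover counts and reasons by arm.

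The cost is wording and some power. With 1% infection in both arms and the Wald limit, power under the joint rule is:

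| OR-to-ED crossover | Power, both required |
|---|---|
| None | 91% |
| 1% | 90.3% to 91.1% |
| 1/13 | about 86% to 90% |
| 1/7 | about 83% to 90% |

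The low end in the last two rows is the case where high-risk children leave OR; at 1/7, as-treated alone would have 85.9% there. If crossover is as rare as the plan expects, the two analyses nearly coincide and the change costs almost nothing.

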Evaluation of the Necessity of Operative Irrigation and Debridement: Pediatric Randomized trial
of type One Open Fractures (PROOF)
[name].

Detailed Project Timeline:

Phase 1 (Pilot phase) :

1. *Mar 2009: pilot (1 center) IRB acceptance Lurie Children's Hospital of Chicago – pilot site*
2. *May 2009: pilot (1 center) recruitment begins*
3. *March 2011: Creation and testing of Survey of attitudes of POSNA membership*
4. *September 2011: Submission of Survey to Evidence Based Medicine Committee*
5. *May 2012: Survey presented to POSNA membership of attitudes*
6. *May 2012: POSNA Clinical Trials Award received*
7. *May 2013: Presentation of POSNA membership attitudes from Survey*
8. *November 2013: Completion of Manuscript of POSNA membership attitudes from Survey*

Phase 2 (Small Multicenter Phase)

9. *November 2011 – April 2012: Recruitment of 3 additional sites (Vancouver Children's Hospital, University of Mississippi Children's Hospital, Riley Children's Hospital)*
10. *May 2012: Investigator's Meeting (POSNA Annual Meeting)*
11. *September 2012: Submission of OREF Clinical Trials Grant*
12. *May 2013: POSNA recruitment meeting for additional sites – attended by 20 centers*
13. *June 2013-September 2013: 7 additional sites agree to join trial (total = 11)*
14. *September 2013: Resubmission of OREF Clinical Trials Grant*
15. *March 2013-January 2014: IRB Submission and Approval (1st 5 secondary sites – Riley Children's, Vancouver Children's, Mississippi Children's, Phoenix Children's, IWK Health Center)*
16. *October 2013: Development of the Manual of Operations*
17. *October 2013: phone conference meeting with centers*
18. *September 2013-November 2013: Data Management System – REDCAP creation*
19. *January 2014: Patient Accrual Begins at 5 sites*
20. *Spring 2014: Interim Analysis. Administrative issues to be discussed with enrollment of patients at various centers and data administration and organization at central center. Improvements to be considered and made. Apply for funding from outside organizations.*

Phase 3 (Large Multicenter Trial Phase):

1. *Sept 2013 – May 2014: IRB Submission and approval at new Phase 3 sites (Mary Bridge Children's Hospital, Yale-New Haven Children's Hospital, Carrie Tingley Children's Hospital, Nationwide Children's Hospital, Denver Children's Hospital).*
2. *Oct 2013- May 2014: Recruitment of final 4 sites*
3. *January 2014: Application for NIH R21 grant if necessary*
4. *May 2014: Award of OREF grant*
5. *April 2014: Investigator's Meeting (POSNA Annual Meeting)*
6. *Spring 2014: Patient Accrual Begins at Phase 3 sites*
7. *Winter 2014: Interim Analysis. Administrative issues to be discussed with enrollment of patients at various centers and data administration and organization at central center. Improvements to be considered and made. Apply for funding from outside organizations.*
8. *April 2014: Investigator Meeting (POSNA Annual Meeting)*
9. *August 2016: Patient Accrual Ends*
10. *December 2016: Follow-up Period End (6 months follow-up)*
11. *January 2017: Data Analysis*
12. *January – April 2017: Manuscript Preparation*

H. Animal Studies: not applicable

I. Human Studies:

The Clinical Trial portion of this study has been approved in pilot form by the Institutional Review Board of Ann & Robert H. Lurie Children's Hospital of Chicago 2009 with a renewal February 2013. IRB#2012-13763

We will submit the Survey Portion of this study for IRB approval once the questions have been tested and finalized among a test group of orthopaedic surgeons.

J. Role of Orthopaedic Surgeon:

The orthopaedic surgeon, a candidate member of POSNA, is the principle investigator for this study. He will be responsible for study hypothesis, study design, study funding, corresponding center recruitment, data maintenance, data interpretation, and publishing the manuscript. Orthopaedic surgeons will be site leaders at all of the additional sites and be responsible for facilitating data collection. All site leaders will be involved in the refinement of study methodology, data analysis, and manuscript preparation.

K. Relevance to Pediatric Orthopaedic Society of North America:

The Pediatric Orthopaedic Society of North America works to provide high quality education for pediatric orthopaedists and to provide the best possible patient care. Fracture management, both closed and open, is extremely common in pediatric orthopaedic surgery. Open fracture management is controversial. The standard of care with open fractures may diverge from clinical practice. If this is the case, either patients are going to the operating room when emergency room treatment will be adequate or they are receiving inadequate care when they avoid operating room management. A clinical trial offers the best evidence to answer this question. Moreover, a fundamental mission of POSNA is to support research that improves the care of pediatric orthopaedic conditions. POSNA has been supportive in creating evidence-based medicine through advocating multicenter prospective studies such as the topic of this proposal

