The family will be instructed to look for signs of infection including increased pain, fevers, or odor coming from the cast. All patients will follow up 5-7 days after the injury where the cast will be windowed and the wound examined. This follow-up appointment is standard of care for all Type I open fractures. Infection will be defined as the Surgical Site Infection by the CDC (see Supplementary information section) guidelines. Signs of infection such as erythema and wound drainage will be treated at the discretion of the attending orthopaedic surgeon with additional antibiotics, local wound care, or formal operative debridement. If no signs of infection are noted then the cast will be repaired. Radiographs will be obtained, as is the standard of care, at all follow up visits. Future follow up visits will not include a routine wound examination unless clinically indicated – fevers, increasing pain, foul odor from cast, etc.

Follow up appointments will be standard of care (non-research related) and will be at approximately 1, 2, 4, 6, 12 and 24 weeks post op.

Informed Consent Process:

If the patient agrees to participate he/she will be formally consented and randomized by calling the study coordinator. The study coordinator, or a representative, will be available 24 hours/day to provide the Parent Permission (consent) form, Adolescent Assent form, and HIPAA Authorization form (if separate from the consent form). At each institution, each participant will be consented using the IRB approved consent and assent forms and HIPAA Authorizations of their institution. The study coordinator, or representative, will have digital copies of each participating institutions' consent forms, assent forms, and HIPAA Authorizations in order to obtain consent remotely at that institution. The study coordinator, or representative, obtaining consent will be listed on the authorized personnel list of the institution that joins the study and has IRB approval to obtain consent with this electronic, remote procedure.

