For the purposes of this study, the video feature will be used for the research coordinator at the lead site to remotely consent patients at other locations. Use of this application for the consent process will only be used at approved sites. This application allows the tablet at one site to call the tablet at the main site through the wireless internet connection. The research coordinator at a given site will create an Apple ID specifically for use on their tablet to login to FaceTime. Patients will not be required to provide an Apple ID or any other sort of personal information in order to use this application. Therefore, no private information of the patient will be saved within the FaceTime application. In agreeing to the use of the tablet for the consent process, participants will be agreeing to the terms of use for the FaceTime application. The patient and/or their parent also have the option to refuse consent via the tablet, in which case a local investigator must consent the patient in person. Additionally, if there are problems with the application or internet connection used to make the call, a study investigator must alternatively consent the patient in person in order for them to be enrolled in the study.

Data Analysis

Ascertainment of response variables:

(Specific Aim 1) An infection will be considered if a return visit to the operating room is necessary for wound complication post randomization and intravenous antibiotics or if the attending surgeon feels that additional antibiotics are necessary, at any time, after the initial seven day course.

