The following are power estimates based on 10000 simulations under the above conditions for various feasible sample sizes. We also obtained power estimates for the scenario involving a 2% infection rate in the control group (OD).

Sample size/arm	Reference Proportion	Power ($\Delta=0.03$)	Power ($\Delta=0.04$)	Power ($\Delta=0.05$)	Power ($\Delta=0.06$)
70	0.01	0.5091	0.6766	0.8536	0.866
80	0.01	0.5164	0.8107	0.8382	0.9434
90	0.01	0.4865	0.786	0.8734	0.9489
100	0.01	0.7416	0.7878	0.9254	0.9616
110	0.01	0.6994	0.8383	0.9245	0.976
120	0.01	0.6926	0.894	0.9437	0.9763
130	0.01	0.714	0.8738	0.9621	0.981
140	0.01	0.6907	0.8783	0.9624	0.99
150	0.01	0.7606	0.9111	0.9748	0.9928
160	0.01	0.8221	0.9394	0.9816	0.997
170	0.01	0.795	0.9427	0.9842	0.998
180	0.01	0.821	0.9339	0.9876	0.9984
190	0.01	0.8147	0.9573	0.9936	0.9987
200	0.01	0.848	0.9629	0.9928	0.9987
210	0.01	0.8503	0.9669	0.9941	0.9995
220	0.01	0.8675	0.9743	0.9961	0.9992
130	0.02	0.4748	0.6378	0.8123	0.9066
140	0.02	0.4906	0.6922	0.8385	0.9288
150	0.02	0.5051	0.7048	0.8785	0.9466
160	0.02	0.5642	0.7452	0.8678	0.9593

170	0.02	0.5458	0.7621	0.8958	0.9679
180	0.02	0.5651	0.7737	0.9165	0.9682
190	0.02	0.5864	0.8088	0.9317	0.9733
200	0.02	0.5865	0.8005	0.9275	0.9807
210	0.02	0.6349	0.8346	0.943	0.9833
220	0.02	0.61	0.842	0.9504	0.9868

For outcome of healing time (**Specific Aim 2**), most fractures have a healing time of 6 weeks with an estimated standard deviation of 1 week. We will again try to show ED management is not inferior with respect to healing time when compared to OR management, assuming a margin of non-inferiority of one week ($\Delta=1$). Assuming a one-sided 0.025 level of significance and power ($1-\beta$) equal to 0.90, the number of subjects required per treatment group can be calculated as follows:

$$H_0: \mu_C - \mu_T \geq \Delta \quad \text{vs.} \quad H_1: \mu_C - \mu_T < \Delta$$

$$N = \frac{2(Z_{\alpha} + Z_{1-\beta})^2 \sigma^2}{\Delta^2}$$

$$N = \frac{2(1.96 + 1.282)^2 1^2}{1^2} \qquad N = 21$$

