Our results suggest that a **sample size of 150 per group (300 total)** would provide 91% power to detect non-inferiority of emergency room management when compared to operating room treatment in the type one open fractures under the assumptions outlined above. We have accepted a 5% infection rate (4% shift from the hypothesized reference rate). If the baseline infection rate is 2%, this study would be adequately powered (87%) to show non-inferiority for a margin of 5% (7% infection rate in the ED arm). As the calculation above illustrates, the study is also well powered to demonstrate non-inferiority with respect to healing time.

Site estimates:

The following sites have provided the initial estimates as to how many patients they feel could be enrolled in a given year: Lurie Children’s = 2/year, Vancouver Children’s Hospital 5/y, Riley Children’s= 2/y, University of Mississippi Medical Center = 9/y, Mary Bridge Children’s Hospital= 12/y, Yale-New Haven Children’s Hospital= 4/y, Carrie Tingley Children’s Hospital= 20/y, Phoenix Children’s Hospital= 20/y, Nationwide Children’s Hospital= 20y, IWK Health Centre, Halifax=4/y, Denver Children’s Hospital=12/y. Texas Children’s Hospital= 12/y, Morristown Medical Center = 2/y, New York University Medical Center = 4/y. Approximate Total= 128/y.

Subject Recruitment:

The number of subjects needed for this trial is large. To date, the pilot study has had an excellent recruitment (80% see below) rate, so we expect similar rates at participating centers.

Currently, with the 14 sites who have agreed to participate thus far, the expected recruitment is 128 patients per year. We plan to add 4-6 more sites during the Planning Grant Period which would expand the projected total recruitment to 160 patients per year. Therefore, when the study is at full capacity, we conservatively anticipate recruiting 120 patients per year (assuming 75% recruitment rate) over the 3 year grant period, for a total of 360 patients, which surpasses the calculated 300 patients needed for adequate statistical power. We are accepting and powering for a 5% infection rate in the ED arm. If we were to accept a 6% infection rate (i.e., a 5% margin of non-inferiority) then we would require only 190 patients. For a 7% infection rate ($\Delta=0.06$), we will need 150 patients. If recruitment is lower than expected, we could accept a larger

margin of non-inferiority given the large range of type I open fracture rate (0-10%) in the literature.

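### The Phase 3 timeline closes follow-up three to five months after accrual ends, short of the stated six months and of the 24-week visit

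*Combined protocol and SAP*

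**What the plan says.** In the Detailed Project Timeline, Phase 3, three consecutive entries read "August 2016: Patient Accrual Ends", "December 2016: Follow-up Period End (6 months follow-up" and "January 2017: Data Analysis". No days of the month are given.

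Under Follow up visit description and schedule, appointments "will be at approximately 1, 2, 4, 6, 12 and 24 weeks post op".

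Two further places bear on what late follow-up is for. Under Ascertainment of response variables, Aim 1 counts an infection after a return to the operating room for a wound complication or "if the attending surgeon feels that additional antibiotics are necessary, at any time, after the initial seven day course", with no upper time limit. The Supplementary Information also gives a CDC surgical site infection definition with a 30-day window. The Data Analysis section compares infection proportions and mean healing times by confidence intervals, and adds Kaplan-Meier curves for infection and healing over the whole of follow-up.

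**The concern.** Six months of follow-up cannot fit between an August end of accrual and a December close, and analysis is scheduled directly afterwards. If the timeline is followed as written, the children enrolled last are analysed without their 24-week visit, so the plan states a length of follow-up that its own dates do not deliver. The documents give no shorter schedule for late enrollees, no common closing date with administrative censoring, and no rule for counting a child whose follow-up is cut short. At stake is whether the infection and healing outcomes are observed for the same period in every child.

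**Working it through.** **Inputs.** End of accrual, end of follow-up and start of analysis come from the Phase 3 timeline. The last visit, at 24 weeks (24 × 7 = 168 days), comes from the visit schedule. The accrual rate comes from Subject Recruitment: "we conservatively anticipate recruiting 120 patients per year (assuming 75% recruitment rate) over the 3 year grant period". The planned total of 300 comes from the sample size section. Assumptions: follow-up is counted from enrolment (treatment is due within about a day), accrual is uniform, and the unstated days of the month are varied from first to last.

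**Step 1: does the stated six months reproduce?** Time available to the last enrolled child:

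| Accrual ends | Follow-up closes | Days | Weeks | Months |
|---|---|---|---|---|
| 1 Aug 2016 | 31 Dec 2016 | 152 | 21.7 | 5.0 |
| 1 Aug 2016 | 1 Dec 2016 | 122 | 17.4 | 4.0 |
| 31 Aug 2016 | 31 Dec 2016 | 122 | 17.4 | 4.0 |
| 31 Aug 2016 | 1 Dec 2016 | 92 | 13.1 | 3.0 |

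It does not. The best case is 168 − 152 = 16 days (2.3 weeks) short of week 24. The month-end case is 168 − 122 = 46 days (6.6 weeks) short.

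**Step 2: when would follow-up be complete?** For a last child enrolled between 1 and 31 August 2016, week 24 falls between 16 January and 15 February 2017. Six calendar months end between 1 and 28 February 2017. Working back from a 31 December close, the latest enrolment date is 16 July 2016 for 24 weeks and 30 June 2016 for six months.

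**Step 3: how many children are affected?** Number = annual rate × days ÷ 365.25, with a 31 December close and 120 per year:

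- Week 24, accrual to 31 August: 120 × 46 ÷ 365.25 = 15.1, or 5% of 300.
- Week 24, accrual to 1 August: 120 × 16 ÷ 365.25 = 5.3, or 2% of 300.
- Six months, accrual to 31 August: 120 × 62 ÷ 365.25 = 20.4, or 7% of 300.

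Sensitivity: at 160 per year, the projection before the 75% recruitment rate is applied, these become about 20, 7 and 27. A close on 1 December instead, at 120 per year, gives about 15 to 25 children missing week 24.

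**Step 4: what is still observed?** A child enrolled on 31 August reaches week 12 on 23 November 2016, before any December close. That covers the 30-day CDC window. For healing, the sample size section assumes that "most fractures have a healing time of 6 weeks with an estimated standard deviation of 1 week", so week 12 lies (12 − 6) ÷ 1 = 6 standard deviations beyond the expected time. Only the 24-week visit is lost.

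**Step 5: how much could infection counts change?** At the assumed 1% rate, 15 to 20 children carry 0.15 to 0.2 expected infections in total, and all of these would be missed only if every infection occurred after the close. In a more severe case, with 5% in the ED arm and 1% in the OR arm, losing every event from 5% of each arm shrinks the 4-point difference by 4 × 0.05 = 0.2 points.

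**The case against.** The strongest reply is that these are month-level projections in a loosely drafted timeline set out under a planning grant heading. It lists an April 2014 investigator meeting twice, for example. The 24-week visit is standard care, no database lock is specified, nothing says that visits stop in December 2016, and the Steering Committee may prolong the study to raise numbers. This stands in part: the documents do not show that late enrollees would go unseen at 24 weeks. But the timeline is the only place that dates the close of follow-up and the start of analysis, and followed as written it omits those visits. The word for approximate timing in the visit schedule does not plausibly absorb a month-end gap of 6.6 weeks, and the timeline itself says six months.

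A reader might infer that the truncation favours non-inferiority, because unseen infections would count as absent. The documents do not support this. They state no such counting rule. Excluding truncated children would cost precision instead, and the Kaplan-Meier curves can accommodate censoring. Allocation is 1:1 in blocks of 4 and 6 within site, so late enrollees should be roughly balanced between arms. Missed events would then lower both rates, and would narrow the difference only if late infections were more frequent in the ED arm.

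A reader might also reason that, with about 3 infections expected in 300 children at 1%, each late one could decide the trial. Few events do make the result sensitive. The relevant number, however, is the events expected among the affected children, at most about 0.15 to 0.2.

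**Conclusion.** The dates contradict each other on every day-of-month reading, and nothing else in the documents reconciles them. The last enrolled child has about 3 to 5 months of follow-up, not six months or 24 weeks. On the assumptions above, with a 31 December close, about 5 to 15 children miss week 24 and up to about 20 miss six months. Exposure is confined to late infections, delayed unions and the tails of the Kaplan-Meier curves. The expected effect on the primary comparison is small and its direction is not established. Sample size and power do not change, since neither calculation uses length of follow-up. This is a minor point, worth correcting because the correction is cheap and, at the version date of 06/01/2015, the affected dates still lay ahead.

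**What to change.** State which length is intended, six months or 24 weeks, and make the timeline agree with it by one of three routes:

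1. **Move the close.** End follow-up on about 28 February 2017 for six months, or 15 February 2017 for 24 weeks, and start analysis after it. From 31 December this costs 59 or 46 days, about six to eight weeks.
2. **End accrual earlier.** Keep the December close, fixed at 31 December, and stop enrolment by 30 June 2016 for six months, or 16 July 2016 for 24 weeks. This costs about 20 or 15 children if accrual would otherwise run to 31 August. On the plan's own projection of 360 recruits, 340 or more would remain, above the 300 needed.
3. **Keep both dates.** Correct the six-month label, state a common closing date with administrative censoring, and say how children with less than full follow-up enter the comparison of proportions. This costs a few sentences and leaves the last enrollees with shorter follow-up.

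None of the three needs new procedures.
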